Synopsis; 4.1 Overall Design; 9.2.1 Decision-Making Framework; 9.5. Interim Analysis	Additional ad hoc interim analyses may be conducted if deemed necessary.	To augment decision making for this JNJ-67864238 intervention cohort.
Synopsis; 9.2.1 Decision-Making Framework; 9.5. Interim Analysis	The number of participants to be included in the interim analysis was updated from at least 45 participants to approximately 45 participants.	To provide flexibility regarding the number of participants required to conduct the interim analysis.
9.2.2.2 Decision-Making Specifics at the Completion of the Intervention Cohort;	A decision-making framework based solely on Crohn's Disease Activity Index scores was added.	To add decision-making criteria based on the primary endpoint of the change in the Crohn's Disease Activity Index from baseline at Week 12.
5.2 Exclusion Criteria, A01; 10.8. Appendix 8: Definition of Minimal Exposure to Ustekinumab	Exclusion criterion A01 was updated to indicate that participants who have had limited exposure to ustekinumab as defined in Appendix 8 may be eligible for this JNJ-67864238 intervention cohort. Appendix 8 was added to specify the definition of minimal exposure to ustekinumab.	To clarify that limited prior exposure to ustekinumab may not disqualify a participant from participating in this JNJ-67864238 intervention cohort.
5.1 Inclusion Criteria 6.5 Concomitant Therapy	Inclusion criterion A06 was added to address the use of COVID-19 vaccines. Guidance was added to address the use of COVID-19 vaccines.	COVID-19 vaccines are provisionally authorized (ie, emergency-use authorization or conditional marketing authorization) and are in use.
10.4 Appendix 4: Liver Safety: Suggested Actions and Follow-up Assessments	The liver safety stopping algorithm and follow-up assessments were updated.	To align with health authority guidance for liver safety.
8.3.7. Adverse Events of Special Interest;	The definition of a possible Hy's law case was added.	To align with health authority guidance for liver safety.

Section number and Name	Description of Change	Brief Rationale

1. PROTOCOL SUMMARY

1.1. Synopsis

Intervention Specific Appendix to Master Clinical Protocol PLATFORMPACRD2001

The following terms are used throughout the Master PLATFORMPACRD2001 synopsis and this 67864238PACRD2001 synopsis:

- "Participant" refers to the common term "subject"
- "Study intervention" refers to study agent, either active or placebo
- "Intervention cohort" refers to a cohort of adult participants with moderately to severely active Crohn's disease who receive a specific active study intervention or the comparator (ie, placebo and/or an active comparator) and in whom the efficacy and safety of that active study intervention is evaluated
- "JNJ-active" and "placebo" refer to the active study intervention and the inactive study intervention, respectively, being tested in an intervention cohort
 - In this intervention cohort, JNJ-active is JNJ-67864238
- "Treatment arm" refers to the treatment assignment within an intervention cohort, eg, JNJ-active, an active comparator, or placebo
- "Control arm" refers to the comparator for JNJ-active, either an active comparator or placebo
- "Intervention Specific Appendix (ISA)" refers to this 67864238PACRD2001 companion protocol to Master protocol PLATFORMPACRD2001, which describes the background information for JNJ-67864238 (eg, preclinical and clinical data), JNJ-67864238 entry criteria or assessments, JNJ-67864238 statistical assessments (eg, sample size, randomization method and ratio), and JNJ-67864238 dosage and administration information.

A platform study is a study with multiple targeted therapies investigated in a single disease in a perpetual manner, with therapies allowed to enter or leave the platform on the basis of a decision algorithm. This ISA describes the Phase 2a study for JNJ-67864238. It is a companion document to the Master protocol PLATFORMPACRD2001, which describes the sponsor's platform study in participants with moderately to severely active Crohn's disease. The Master protocol PLATFORMPACRD2001 describes the common study design elements and this ISA describes additional protocol elements specific to JNJ-67864238.

JNJ-67864238 is an oral antagonist of the interleukin (IL)-23 receptor (IL-23R) being developed for the treatment of moderately to severely active Crohn's disease. **CCI**

Targeting of the IL-23 pathway has shown to be effective in the treatment of Crohn's disease in clinical studies. Selective inhibition of IL-23R with an oral compound offers an additional opportunity to uniquely inhibit IL-23 driven pathology.

JNJ-67864238 is also known as PTG-200 and will be referred to as JNJ-67864238 in this ISA protocol synopsis.

OBJECTIVES AND ENDPOINTS

Refer to the synopsis of the Master protocol PLATFORMPACRD2001 for study objectives and endpoints.

Hypothesis

Refer to the synopsis of the Master protocol PLATFORMPACRD2001 for the study hypothesis.

OVERALL DESIGN, INTERVENTION COHORT AND DURATION, AND NUMBER OF PARTICIPANTS

The overall study design and target population are presented in the synopsis of the Master protocol PLATFORMPACRD2001. This ISA is designed to assess the effects of a predominantly gastrointestinal-restricted anti-IL-23R compound, JNJ-67864238, for moderately to severely active Crohn's disease. This 12-week Phase 2a study is focused on proof-of-concept and will assess the safety and efficacy of an orally administered high dose of JNJ-67864238 compared with placebo in participants with Crohn's disease. Since the inhibition of the IL-23 pathway has been validated as a mechanism for treating Crohn's disease, a high dose was chosen to assess the efficacy of a locally acting anti-IL-23 inhibitor.

Participants may be biologic intolerant or refractory (Bio-IR) or biologic nonfailures (Bio-NF) populations as defined in the synopsis of the Master protocol PLATFORMPACRD2001.

A target of 90 Bio-IR and Bio-NF participants will be randomized to receive JNJ-67864238 [CC1] [REDACTED] or placebo in a 3:2 ratio using permuted block randomization, stratified by baseline Crohn's Disease Activity Index (CDAI) score (≤ 300 , > 300) and biological refractory status (Bio-IR, Bio-NF). The treatment arms for this study will be as follows:

- JNJ-67864238 [CC1] [REDACTED] (N=54)
- Placebo (N=36)

Of note, the sample size has been chosen to assess a level of efficacy consistent with that observed with systemically available biological therapies for Crohn's disease.

There is 1 database lock planned at the end of this intervention cohort. In addition, there will be a planned Interim Analysis (IA) to enable early termination of the intervention cohort if JNJ-67864238 ([CC1] [REDACTED]) is futile. Additional ad hoc IA(s) may be conducted if deemed necessary. No database locks are planned for any of the IA(s).

Refer to the synopsis of the Master protocol PLATFORMPACRD2001 for a description of the Data Monitoring Committee.

End of Study Definition

The end of the JNJ-67864238 intervention cohort is considered as the last visit for the last participant in the intervention cohort. Refer to the synopsis of the Master protocol PLATFORMPACRD2001 for the end of study definition.

Description of Study Interventions

Dosage and Administration Specifics for JNJ-67864238 and Matching Placebo		
	JNJ-67864238	Placebo
Dosage formulation	A solid dosage formulation of JNJ-67864238 supplied as 300 mg oral tablets Refer to the Investigator's Brochure for a list of excipients	Matching placebo oral tablets
Unit dose strength(s)/ Dosage levels:	300 mg oral tablets	Matching placebo oral tablets
Route of administration	Oral	Oral
Dosage instructions	JNJ-67864238 CCI [REDACTED]	Matching placebo CCI [REDACTED]
Packaging and labeling	JNJ-67864238 will be packaged in blister packs. The study supplies will be packaged according to the randomization code and each unit will be labeled with a medication ID number. JNJ-67864238 will be dispensed in child-resistant packaging. JNJ-67864238 labels will contain information and be labeled as required per country regulatory requirements. Labels must remain affixed to the container.	Matching placebo will be packaged in blister packs. The study supplies will be packaged according to the randomization code and each unit will be labeled with a medication ID number. Matching placebo will be dispensed in child-resistant packaging. Matching placebo labels will contain information and be labeled as required per country regulatory requirements. Labels must remain affixed to the container.
Preparation, handling, and storage	All JNJ-67864238 will be stored in a secure area with restricted access. The JNJ-67864238 solid dosage formulation must be stored at controlled temperatures as indicated on the product specific labeling.	All matching placebo will be stored in a secure area with restricted access. The matching placebo must be stored at controlled temperatures as indicated on the product specific labeling.

EFFICACY EVALUATIONS

There are no intervention-specific efficacy evaluations. Refer to the synopsis of the Master protocol PLATFORMPACRD2001 for efficacy evaluations.

PHARMACOKINETIC EVALUATIONS

Plasma and fecal samples will be used to evaluate the systemic and local colon exposure, respectively, of JNJ-67864238. Plasma collected for pharmacokinetics may additionally be used to evaluate safety or efficacy aspects that address concerns arising during or after the study period. In addition, biopsy samples will be used for the measurement of JNJ-67864238 tissue concentration.

IMMUNOGENICITY EVALUATIONS

Immunogenicity will not be assessed in the JNJ-67864238 intervention cohort. Samples collected for immunogenicity would only be analyzed if required to assess other data or analyses, such as pharmacokinetics or adverse events.

PHARMACODYNAMIC AND BIOMARKER EVALUATIONS

Pharmacodynamic assessments will be made to examine the biological response to treatment and to identify genes and proteins that are relevant to JNJ-67864238 treatment and/or Crohn's disease. Serum, fecal, and whole blood samples will be collected from all participants to study the effect of JNJ-67864238 on proteins (serum and fecal samples) and RNA expression (whole blood and biopsy samples). Stool and saliva samples will also be collected to evaluate the effects of JNJ-67864238 on the microbiome.

PHARMACOGENOMIC (DNA) EVALUATIONS

Among participants who consent separately to this component of the study, whole genome analyses will be performed to detect associations between specific gene polymorphisms to the disease or JNJ-67864238 response. DNA analysis will be restricted to JNJ-67864238-related effects or to the diseases for which JNJ-67864238 is being developed.

SAFETY EVALUATIONS

Participants will be screened for tuberculosis (TB) at study entry. In addition, to aid in the early detection of TB reactivation or new TB infection during study participation, participants must be evaluated for signs and symptoms of active TB at scheduled visits.

Refer to the synopsis of the Master protocol PLATFORMPACRD2001 for other safety evaluations.

STATISTICAL METHODS

Sample Size Determination

The decision-making framework is applied to a total of 5000 virtual studies with simulated CDAI and change in the Simplified Endoscopic Score for Crohn's disease (SES-CD) data. With 90 participants (54 participants receiving JNJ-67864238 **CCI** [REDACTED] and 36 participants receiving placebo), under the alternative hypothesis, the probability of JNJ-67864238 meeting the success criteria is approximately 87%, and the probability of dropping JNJ-67864238 for futility is approximately 1%. When there is no treatment difference, the probability of JNJ-67864238 meeting the success criteria is approximately 5% and the probability of dropping JNJ-67864238 for futility is approximately 77%. There is approximately a 32% chance that the futility criteria are met at the IA.

For reference, without factoring in the interim futility analysis, the sample size of 90 participants (54 participants in the JNJ-67864238 **CCI** [REDACTED] treatment arm and 36 participants in the placebo treatment arm) will provide 90% power to detect a treatment difference at $\alpha=0.1$ (2-sided) when the true treatment difference is 60 (placebo – JNJ-67864238) in the change in CDAI at Week 12 for both Bio-IR and Bio-NF populations.

Efficacy Analyses

There are no JNJ-67864238-specific efficacy analyses. Refer to the synopsis of the Master protocol PLATFORMPACRD2001 for efficacy analyses.

Safety Analyses

[figure not shown]
There are no JNJ-67864238-specific safety analyses. Refer to the synopsis of the Master protocol PLATFORMPACRD2001 for safety analyses.

Interim Analyses

One IA is planned. It will take place when approximately 45 participants have completed their Week 12 assessments or have withdrawn early from the intervention cohort. Additional ad hoc IA(s) may be conducted if deemed necessary. The objective of the IA(s) is to enable early termination of the intervention cohort if JNJ-67864238 is futile and plan for future intervention cohorts. At the time of the IA(s), the study team will remain blinded. The planned IA (and any additional IA[s]) will be described in the IA SAP.

1.2. Schema

Figure 1: Schematic Overview of Study Design

1.3. Schedule of Activities

A consolidated Schedule of Activities for the Master protocol PLATFORMPACRD2001 and this ISA is presented in [Table 1](#).

Table 1: Consolidated Schedule of Activities - PLATFORMPACRD2001 and 67864238PACRD2001										
67864238PACRD2001 specific events	Period	Screening ^a	Treatment Phase ^b				Early Termination ^c	Final Safety Follow-up ^d		
			Week	-5 weeks	0	2	4	8	12	
Study Procedures										
Screening/Administrative										
Informed consent ^e		X								
Master protocol inclusion/exclusion criteria ^f		X		X						
X JNJ-67864238 inclusion/exclusion criteria ^f		X		X						
Medical history and demographics		X								
Immunization history		X								
Stool studies to evaluate for enteric pathogens ^g				X						
Height		X								
X^v QuantiFERON-TB test		X								
X^w Chest radiograph		X								
HIV, HBV and HCV testing		X								
Follicle stimulating hormone test (optional at the discretion of the investigator)				X						
Serum pregnancy test ^h		X								
X (Week 4 only) 12-lead ECG		X			X		X	X		
Training on diary completion		X								
Randomization				X						
Study Intervention Administration										
X Dispense study intervention				X	X	X	X			
X Administer study intervention				Daily Self-Administration						
X Study intervention accountability				X	X	X	X	X		
Safety Assessments										
Physical examination		X				X	X	X		

Table 1: Consolidated Schedule of Activities - PLATFORMPACRD2001 and 67864238PACRD2001									
67864238PACRD2001 specific events	Period	Screening ^a	Treatment Phase ^b					Early Termination ^c	Final Safety Follow-up ^d
			Week	-5 weeks	0	2	4	8	12
Study Procedures									
Body weight		X		X	X	X	X	X	X
Vital signs ⁱ		X		X	X	X	X	X	X
Urine pregnancy test ^j				X	X	X	X	X	X
Concomitant therapy review		X		X	X	X	X	X	X
Adverse events review		X		X	X	X	X	X	X
X^x Tuberculosis evaluation/other infection assessment		X		X	X	X	X	X	X
Efficacy Assessments									
Collect and review diary entries ^k				X	X	X	X	X	X
X^{bb, cc} CDAI assessments ^{l, m}		X		X	X	X	X	X	X
Fistula exam				X	X	X	X	X	X
Abdominal pain NRS assessment ⁿ				X	X	X	X	X	X
Stool sample (fecal lactoferrin and calprotectin) ^o		X		X	X	X	X	X	X
X^y Video ileocolonoscopy with biopsies for RNA and histology ^p		X						X	X
PROMIS-29 ^q				X				X	X
PGIC								X	X
PGIS				X				X	X
Clinical Laboratory Assessments									
Hematology ^{r, s}		X		X	X	X	X	X	X
Chemistry ^{r, s}		X		X	X	X	X	X	X
CRP		X		X	X	X	X	X	X
Pharmacokinetics/Immunogenicity									
X^z Plasma JNJ-67864238 concentration ^t				X	X	X	X	X	X
X^z Serum antibodies to JNJ-67864238 ^t				X		X		X	X
X^{aa} Fecal samples for stool concentrations of JNJ-67864238 ^t					X	X	X	X	X
Pharmacodynamics/Biomarkers									
Whole blood samples for biomarkers ^t		X		X	X	X	X	X	X
Serum samples for biomarkers ^t		X		X	X	X	X	X	X
X^{aa} Fecal samples for biomarkers ^t		X ^p		X	X	X	X	X	X
Saliva samples for microbiome ^t				X				X	X

Table 1: Consolidated Schedule of Activities - PLATFORMPACRD2001 and 67864238PACRD2001											
67864238PACRD2001 specific events	Period	Screening ^a	Treatment Phase ^b					Early Termination ^c	Final Safety Follow-up ^d		
			Week	-5 weeks	0	2	4	8	12		
	Study Procedures										
	Pharmacogenomics (DNA)										
	Whole blood samples for DNA analysis ^u			X							

Abbreviations: CDAI=Crohn's Disease Activity Index; CRP=C-reactive protein; DNA=deoxyribonucleic acid; ECG=electrocardiogram; HBV=hepatitis B virus; HCV=hepatitis C virus; HIV=human immunodeficiency virus; NRS=numeric rating scale; PGIC= Patient's Global Impression of Change; PGIS= Patient's Global Impression of Severity; PROMIS=Patient-Reported Outcomes Measurement Information System; RNA=ribonucleic acid; TB=tuberculosis.

Footnotes:

- a. The screening period should be a minimum of 7 days to allow for collection of CDAI data. Participants who are rescreened do not need to have a minimum of 7 days, provided that they have enough data to support CDAI calculation. The screening period should be a maximum of 5 weeks.
- b. Visit windows should be \pm 4 days for each visit.
- c. A participant will not be automatically withdrawn if they discontinue the study intervention before the end of the intervention cohort. Participants should return for all scheduled visits including the final safety follow-up visit.
- d. All participants should complete a final safety follow-up visit after their last study intervention administration. The safety follow-up period after the last dose of the study intervention should be 4 weeks.
- e. Informed consents for both the Master protocol and the Intervention Specific Appendix must be signed before first study-related activity.
- f. Minimum criteria for the availability of documentation supporting the eligibility criteria are described in Source Documentation in Appendix 5 of the Master protocol PLATFORMPACRD2001, Regulatory, Ethical, and Study Oversight Considerations. Check clinical status again before first dose of study intervention.
- g. Stool studies for enteric pathogens may be performed at either the central or a local laboratory and must include a stool culture and Clostridium difficile toxin assay. These must have been performed within 4 months before Week 0. Additional testing, such as ova and parasites or Escherichia coli O157:H7 assessment may be performed at the investigator's clinical discretion.
- h. Must be performed before any administration of the study intervention for female participants of childbearing potential.
- i. Temperature, pulse/heart rate, respiratory rate, and blood pressure.
- j. Must be performed at every visit for female participants of childbearing potential.
- k. For all visits up to and including Week 12, daily diary information should be collected for every day prior to each visit.
- l. Hematocrit value obtained during screening will be used to calculate CDAI at Week 0.
- m. CDAI will calculated using the total number of liquid or very soft stools in the previous 7 days. During the screening visit, participants should be trained on how to complete the CDAI diary, including instructions that only liquid and very loose stools should be scored using the Bristol Stool Form Scale as a reference.
- n. Participant will complete the abdominal pain numeric rating scale (NRS) assessment as a daily diary entry, beginning during screening, and bring the diary to each visit. For all visits up to and including Week 12, daily diary information should be collected for every day prior to the visits. Patient-reported outcome components of the CDAI should be performed first (ie, before the NRS).
- o. Stool samples required for the visits with a video ileocolonoscopy should be obtained before the start of the bowel preparation for the video ileocolonoscopy that is also scheduled for the visit.
- p. Because these procedures must not interfere with the collection of CDAI data, if performed on the day of these visits, the 7 days before the initiation of the colonoscopy preparation should be used to calculate CDAI scores for these visits. If the video ileocolonoscopic examination is not performed on the day of the

visit, it must be performed at least 8 days before the Week 0 visit and no more than 8 days before the Week 12 visit or early termination visit. The Simplified Endoscopic Score for Crohn's disease (SES-CD) will be calculated by the central reader.

- q. The PROMIS surveys should be administered before any clinical procedures or tests are performed. PROMIS surveys will only be collected in countries where translations are available.
- r. Hematology and chemistry tests at Week 0 are not required if screening laboratory tests were performed within 2 weeks before the Week 0 visit.
- s. Blood samples should be collected after PROs are administered and vital signs collected. All reasonable attempts should be made to collect samples at the scheduled timepoints and record the actual times of sample collections.
- t. All reasonable attempts should be made to collect samples at the scheduled timepoints and record the actual dates and times of sample collections.
- u. Requires completion of a separate informed consent.

67864238PACRD2001 specific

- v. All participants will undergo QuantiFERON-TB testing. In countries where the QuantiFERON-TB test is not registered/approved, TB skin testing will also be required (recommended but not required for study centers in Ukraine if tuberculin is not available).
- w. Chest radiograph (posterior-anterior view) must be obtained within 3 months before the Week 0 visit.
- x. If TB is suspected at any time, a chest radiograph and QuantiFERON-TB test should be performed. In countries where the QuantiFERON-TB test is not registered/approved, TB skin testing should also be performed (recommended but not required for study centers in Ukraine if tuberculin is not available).
- y. Biopsy samples will also be used for the measurement of JNJ-67864238 tissue concentration.
- z. Venous blood samples of sufficient volume for the measurement of JNJ-67864238 plasma concentrations and to assess serum antibodies to JNJ-67864238 will be collected from all randomized participants as follows:
 - Before study intervention administration (ie, predose) at Week 0, Week 2, Week 4, Week 8, and Week 12
 - i. The Weeks 2 and 8 sample should be of sufficient volume to assess the plasma concentration of JNJ-67864238 (and a backup sample).
 - ii. The Weeks 0, 4, and 12 samples should be of sufficient volume to assess the plasma concentration of JNJ-67864238 (and a backup sample) and to assess serum antibodies to JNJ-67864238.
 - After study intervention administration (ie, postdose) at Week 12 within 2 to 4 hours
 - At the early termination visit (if applicable)
- aa. A single stool sample (ie, bowel movement) will be collected at each visit to assess JNJ-67864238 stool concentration and biomarkers.
- bb. At the screening visit only, the CDAI will be calculated using participant recall. The investigator will complete the variable assessments required to calculate the CDAI total score as conducted in the other visits.
- cc. For visits other than Week 0, the most recent hematocrit value obtained before a visit will be used to calculate the CDAI for that visit.

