#### 5.3.1. Definition of Endpoint

The primary endpoint will be change from baseline in the CDAI score at Week 12 based on full analysis set. This will apply for both interim analysis and final analysis.

The CDAI is a validated multi-item measure of severity of illness derived as a weighted sum of 8 different Crohn’s disease-related variables. These 8 variables are:

- extra-intestinal manifestations
- abdominal mass
- weight
- hematocrit
- use of antidiarrheal drug(s) and/or opiate
- total number of liquid or very soft stools
- abdominal pain/cramps

- general well-being.

The last 3 variables are scored over 7 days by the participant on a diary card. For the total number of liquid or very soft stools, abdominal pain/cramps, and general well-being, if only 5 days or 6 days of data are available for the calculation, the weights of 7/5 and 7/6, respectively, will be used for the calculation; if the values are recorded for less than 5 days, the component will not be calculated.

At each timepoint, the CDAI score will only be calculated if  $\geq 4$  of the 8 components are available. If the CDAI score cannot be calculated (ie,  $<4$  components available), the CDAI score will be considered missing. When at least 4 of the 8 components are available, any missing components will be imputed by carrying forward the last non-missing component.

The weight component of the CDAI will be based on the standard weight table (Attachment 5).

Subjects who do not return for evaluation or have a missing CDAI score at Week 12 will be considered to have no change at Week 12 from their baseline CDAI score.

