## Attachment 3: Crohn's Disease Activity Index

DISEASE ACTIVITY INDEX	SUM	X FACTOR	SUBTOTAL
Total number of liquid or very soft stools in the previous 7 days		x 2 =	
Sum abdominal pain/cramps ratings (total for previous 7 days): 0 = none      2 = moderate 1 = mild      3 = severe		x 5 =	
General well being (total for previous 7 days): 0 = generally well      3 = very poor 1 = slightly under par      4 = terrible 2 = poor		x 7 =	
Categories currently present and presumed to be related to Crohn's disease: 0 = no; 1 = yes			
Y = arthritis/arthralgia		x 20 =	
Y = iritis/uveitis		x 20 =	
Y = erythema nodosum/pyoderma gangrenosum/aphthous stomatitis		x 20 =	
Y = anal fissure, fistula or abscess		x 20 =	
Y = other fistula		x 20 =	
Y = fever over 100° F (37.8° C) during the previous 7 days.		x 20 =	
During the previous 7 days has participant received antidiarrheal therapy at least once:			
OR			
During the previous 7 days has participant received opiate therapy on each of the 7 days: 0 = no 1 = yes		x 30 =	
Abdominal mass: 0 = none    2 = questionable    5 = definite		x 10 =	
Hematocrit: Males: (47-Hct) = SUM Females: (42-Hct) = SUM		x 6 = (add or subtract by sign)	
		*	
$\frac{(\text{Standard Weight} - \text{Actual Body Weight})}{\text{Standard Weight}} \times 100 =$		x 1 =	
		(add or subtract by sign, round to 3 decimal places)	
* If this value is less than -10 then enter -10 here. Standard weight and actual weight must be in same units (kg or lb)			
		TOTAL =	
		(round total to integer)	

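### An off-day colonoscopy 1 to 7 days before the Week 12 visit falls inside the 7-day CDAI diary look-back, and no supplied rule excludes the affected days

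*Protocol*

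**What the plan says.** Protocol Section 1.3, Table 1, footnote p opens with its purpose: "Because these procedures must not interfere with the collection of CDAI data". It then covers three situations.

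- **Procedure on the visit day:** "if performed on the day of these visits, the 7 days before the initiation of the colonoscopy preparation should be used" for the CDAI.
- **Procedure on another day, Week 0:** a minimum gap of 8 days.
- **Procedure on another day, Week 12 or early termination:** a maximum gap of 8 days. The limits for both off-day cases stand in one clause: "it must be performed at least 8 days before the Week 0 visit and no more than 8 days before the Week 12 visit".

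The default look-back is in footnote m: "CDAI will calculated using the total number of liquid or very soft stools in the previous 7 days". The scoring form in SAP Attachment 3 repeats it: "Total number of liquid or very soft stools in the previous 7 days". Footnote k requires the diary without exception: "For all visits up to and including Week 12, daily diary information should be collected for every day prior to each visit".

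SAP 5.3.1 deals only with diary days that are not available: "if only 5 days or 6 days of data are available for the calculation, the weights of 7/5 and 7/6, respectively, will be used", and "if the values are recorded for less than 5 days, the component will not be calculated". It does not address preparation or procedure days. Protocol Section 8.1 refers to the Master protocol for efficacy assessments, and that document was not supplied.

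**The concern.** A minimum gap protects a look-back window; a maximum gap does not. At Week 12 an off-day procedure may fall on any of the 7 days that the CDAI counts. The shifted look-back does not help, because it is conditional on a same-day procedure. A programmer who follows footnote m and Attachment 3 would count the liquid stools caused by bowel preparation, at 2 points each.

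Baseline is protected and Week 12 is not, so the artefact does not cancel in a participant's change from baseline, which is the primary variable. It acts in one direction, making Week 12 look worse. It also enters Week 12 remission (CDAI below 150) and response. PRO-2 remission uses the same diary items and may move the same way; that is not quantified here.

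**Working it through.** **Calendar check.** Take the visit as day 0 and the look-back as the 7 preceding days. The procedure is k days before the visit. The documents give no preparation length, so one and two days are both shown as assumptions.

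| k | Look-back days affected, one-day preparation | Two-day preparation |
|---|---|---|
| 1 to 5 | 2 (5 clean) | 3 (4 clean) |
| 6 | 2 (5 clean) | 2 (5 clean) |
| 7 | 1, procedure day only (6 clean) | 1 (6 clean) |
| 8 | 0 | 0 |

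Of the permitted off-days, only day 8 is clean. If the visit day itself were counted in the window, the exposed range would be 1 to 6. Week 0 off-day procedures (8 days or more) and same-day procedures with the shifted window have no overlap.

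**The plan's own power figure.** SAP Section 3 gives about 90% for a difference of 60 and SD 93; protocol 9.2.3.2 gives 54 and 36 participants and a two-sided alpha of 0.1. The noncentrality is 60 / (93 × √(1/54 + 1/36)) = 60 / 20.01 = 3.00 on 88 degrees of freedom, giving power of 90.8%. The figure is reproduced.

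**Inputs for the size of the effect.** Protocol Appendix 6 gives mean CDAI at Weeks 0 and 12 of 323 to 238 (active) and 298 (placebo) for Bio-IR, and 302 to 176 and 236 for Bio-NF. The populations are split 50:50 and the Week 12 variance is 11025 (SD 105). Planned mean changes are (−85 − 126)/2 = −105.5 active and (−25 − 66)/2 = −45.5 placebo.

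*Assumptions, not in the documents:* each affected participant gains the same shift in either arm. The low case is 5 extra liquid stools × 2 = 10 points. Higher cases are 8 × 2 + 5 = 21 and 15 × 2 + 15 = 45, the additions being for pain and well-being, with 30 as an intermediate value. The affected share f is 10%, 25% or 50% of those with an observed Week 12 score.

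**Remission without a shift.** P(CDAI < 150) = Φ((150 − mean)/105).

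- Active: Φ(−88/105) = 20.1% and Φ(−26/105) = 40.2%, average 30.2%.
- Placebo: Φ(−148/105) = 7.9% and Φ(−86/105) = 20.6%, average 14.3%.
- Difference: 15.9 percentage points.

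**With a shift.** Add the shift to each mean, then mix: (1 − f) × unshifted + f × shifted. For power, SD = √(93² + f(1 − f) × shift²).

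| Shift | Improvement understated in each arm, points (f = 10/25/50%) | Remission difference, points | Primary power, % |
|---|---|---|---|
| +10 | 1.0 / 2.5 / 5.0 | 15.8 / 15.6 / 15.3 | 90.8 / 90.8 / 90.8 |
| +21 | 2.1 / 5.3 / 10.5 | 15.6 / 15.3 / 14.7 | 90.7 / 90.6 / 90.5 |
| +30 | 3.0 / 7.5 / 15.0 | 15.5 / 15.0 / 14.1 | 90.6 / 90.4 / 90.2 |
| +45 | 4.5 / 11.3 / 22.5 | 15.4 / 14.6 / 13.3 | 90.3 / 89.7 / 89.4 |

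The remission difference falls by 0.1 to 2.6 points. Truncating baseline to the entry range of 220 to 450 gives unshifted remission of about 28% and 13% and a largest fall of 2.8 points, so about 2.7 covers both. Response, computed the same way with the Appendix 6 covariances, falls from a difference of 23.7 by at most 2.2 points. Power falls by at most about 1.4 points.

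**Treatment failures.** They receive baseline values (SAP 5.3.1), so the overall effect is smaller. If 10% to 20% fail (assumption), 7.5 points becomes 7.5 × 0.9 = 6.8 to 7.5 × 0.8 = 6.0.

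**The case against.** The strongest case against this concerns its size and the unseen source. Table 1 places the colonoscopy at the Week 12 visit, so off-day procedures may be uncommon and the 25% and 50% shares may be far too high. The stool counts are assumed, and the full shift overstates the case of a procedure 7 days before, where a one-day preparation lies outside the window. The population-level summary of the primary estimand is the difference between arms, which an equal shift leaves alone. The largest remission loss is small against a standard error of about 8.5 points for 54 versus 36 participants. Footnote p also appears to be common Master text, since the cohort-specific footnotes start at v, and Master Section 8.1 may hold the missing rule.

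All of this limits the consequence, and it stands. It does not supply a rule: the purpose sentence in footnote p states an aim but does not say which diary days to use for an off-day Week 12 procedure.

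Three stronger readings are tempting but unsupported:

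- **That the success or futility decision is biased.** That needs timing to differ between arms, and the documents give no reason to expect it. For scale, a 10-percentage-point imbalance would move the mean difference by 0.10 × 10 = 1.0 to 0.10 × 45 = 4.5 points.
- **That the trial has no rule at all.** Only the supplied documents can be judged.
- **That every early termination visit corrupts the endpoint.** Under SAP 5.1.1, visits before Day 71 do not supply the Week 12 value, and treatment failures receive their baseline score whatever was observed.

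**Conclusion.** The point holds on the supplied text and is minor. Footnote p protects the diary at Week 0 and for same-day procedures, but for off-day procedures at Week 12 or early termination its rule does not achieve its own stated aim. Improvement, remission and response at Week 12 are understated within arms by an amount that the documents do not allow to be estimated. The ranges above illustrate scale and are not a forecast; they rest on the assumed shift, share and preparation length. If procedure timing is balanced between arms, the mean CDAI difference, and so its comparison with the 40 and 60 thresholds, is not biased, and the primary analysis gains only slight noise. The remaining uncertainty is whether the Master protocol already settles the matter.

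**What to change.** In footnote p and SAP 5.3.1, extend the existing same-day rule. Whenever a preparation or procedure day falls in the 7 days before the Week 12 visit, or before an early termination visit whose CDAI is analysed, score the CDAI diary items and PRO-2 from the 7 days before preparation started. If the Master protocol already has this rule, cross-refer to it. Settle the wording before unblinding.

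The cost is one sentence in the footnote and one derivation rule. Footnote k already requires a daily diary, so no new data are needed. The downside is an older diary window. With a one-day preparation it covers days k + 2 to k + 8 before the visit, so it ends 3 to 9 days before the visit; for a procedure 7 days before, it covers days 9 to 15.

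Treating the affected days as unrecorded and applying the 7/5 and 7/6 weights is not a good substitute. A two-day preparation with the procedure 1 to 5 days before leaves only 4 diary days, so the diary components would not be calculated. Five of the 8 components would remain, above the minimum of 4, and SAP 5.3.1 would then carry forward an earlier visit's diary components.
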